13.3.4 Reporting of Serious Adverse Events

8.3.4.1 Reporting of SAEs to the Sponsor

It is the responsibility of the PI to insure all SAEs and follow-up SAEs, occurring from the signature of the ICF until the 18-month follow-up visit, are reported to the Sponsor or Sponsor's designee within 24 hours of discovery or notification of the event or the follow-up information. For each SAE and follow-up to an SAE the site should ensure that critical AE CRFs are completed as of the onset date for the SAE (e.g. demographics, concomitant medications, and medical history) as described in the Study Reference Manual.

At any time after completion of the AE reporting period, if the Investigator becomes aware of an SAE that is suspected by the Investigator to be related to the investigational product, the SAE must be reported to the Sponsor or Sponsor's designee within the same timelines.

SAEs shall be sent to CTI Safety preferably by Facsimile transmission, via secure e-fax specific to this study, with the SAE Report Form. In circumstances where facsimile equipment is not available, notification by email to [contact] is acceptable.

SAEs shall be sent by eFAX with the SAE report form to: CTI Safety

Drug Safety Country-Specific Contact Numbers

Country	E-Fax	SAE Hotline
United States	[name]	[contact] / [contact]
Sweden	[name]	
CTI GSP EMAIL	[contact]	

In circumstances where it is not possible to send the notification by the above-mentioned method, notification by telephone is acceptable, with a copy of the SAE Report Form sent by overnight mail. Initial notification via the telephone does not replace the need for the investigator to complete, sign and send the SAE form within the time frames outlined above.

8.3.4.2 Reporting of SAEs to Competent Authorities

SAEs that are considered as possibly or probably related to the investigational product, and as unexpected, will be reported to the Competent Authorities by the Sponsor or Sponsor's designee as required by applicable local regulations; therefore it is critical that site personnel record SAEs in the eCRF in a timely manner. Per regulation, any unexpected fatal or life-threatening AEs assessed as possibly or probably related to NKA will be reported to the Competent Authorities by the Sponsor or Sponsor's designee within 7 calendar days. Additional information will be reported to the Competent Authorities within an additional 8 calendar days. The Sponsor or Sponsor's designee is required to submit any other unexpected SAEs assessed as possibly or probably related to NKA to the Competent Authorities within 15 calendar days of notification.

13.4 Events of Special Interest

The following events are considered "events of special interest" as they are events that have been reported in the past following one or more of the procedures performed during this study. Patients should be carefully monitored for appearance of these events at any time during the study.

13.4.1 Procedure-related Events

Post-procedure Pain: If the subject experiences pain following the biopsy or injection, simple analgesia with paracetamol or paracetamol-codeine combinations usually suffices to control the pain. More severe pain in the loin or abdomen requires ultrasonography to exclude significant perirenal hemorrhage. Patients will be followed with regular hemoglobin and blood pressure monitoring. If severe pain occurs, opiates may be necessary. If analgesic doses higher than the maximum authorized doses are required to alleviate pain, then the Investigator must perform additional clinical evaluations to ascertain the probable cause(s) of excessive pain.

Hemorrhage: A degree of perirenal bleeding accompanies almost every renal biopsy. According to the literature (Whittier and Korbet, 2004b), mean hemoglobin decreases approximately 1.0 g/L to about 10 g/L after injection biopsy. Macroscopic hematuria and painful hematomas are seen in about 3 % of patients after renal biopsy. Therefore, following the biopsy and injection, patients will be followed with regular hemoglobin and blood pressure monitoring. Patients will be confined to bed and monitored for maintenance of normal coagulation indices. If bleeding is brisk and the patient is hypotensive despite bed rest, blood transfusion will be considered. If the bleeding is still not controlled, surgery may be considered. In rare cases, renal angiography should be performed to identify the source of bleeding and coil embolization can be performed in such cases during the same procedure. **Arteriovenous (AV) fistula:** According to the literature (Abutaleb and Obaideen, 2007; Arora et al., 2012; Ham et al., 2012; Huang et al., 2011; Whittier and Korbet, 2004a; Whittier and Korbet, 2004b), AV fistulas can be found in about 18% of patients that have undergone renal biopsy. However, as more than 95% of these resolve within 2 years, they should not be routinely pursued. If patients have recurrent hematuria after a renal biopsy or injection, AV fistulas could be considered. In these cases embolization may be indicated. If an AV fistula is detected by ultrasound at the pre-injection qualification visit, then the PI should consider discontinuing the patient prior to injection.

Other complications: In very rare cases other organs, such as liver, gallbladder and lungs may have been penetrated during the procedure. In these cases appropriate treatment and follow-up will be discussed with surgeons.

Death: Deaths resulting from renal biopsies occur in <0.01% of patients (Hergesell et al., 1998; Lin et al., 2006; Walker, 2009) but could be due to uncontrolled bleeding especially in patients with severe renal impairment. Strict inclusion/exclusion criteria will be followed to ensure that patients who may be predisposed to uncontrolled bleeding would not be enrolled in the trial.

13.4.2 Product-related Events

No product-related events are expected to occur. This is based on the autologous nature of NKA (i.e., NKA is manufactured from renal cells isolated from the same kidney to which they are to be returned), the lack of product-related events observed in the animal studies, and the lack of specific NKA related events seen during and following injection of the first 5 patients in Sweden (See Section 6.5.1). However, patients will be extensively monitored throughout the course of the study for any unexpected events. If an event occurs which is assessed as related to the investigational product, NKA, then the event will be immediately reviewed by the Medical Monitor and PI.

13.5 Data Safety Monitoring Board

Given the uniqueness of this product, an external data safety monitoring board (DSMB) will be convened to oversee patient safety, especially as it relates to any unexpected product-related events. The committee will be composed of a minimum of 3 members whose expertise is such that the Board has adequate familiarity with reconstructive urological surgery, renal medicine, and monitoring emerging safety issues in clinical studies. The DSMB will be an independent committee that is not otherwise engaged in the conduct of the clinical study and who do not have conflicts of interest.

The DSMB will be governed by the DSMB charter. The specific mandate of the DSMB will be to review any AE's/SAE's assessed by the PI as related to the investigational product, NKA. Thus, any events assessed as related to NKA will be forwarded to the DSMB by the study site or CRO. If the event is rated mild or moderate, the DSMB will work with the PI and Medical Monitor to determine the best course of action. The "best course of action" may range from no changes to adaptations of procedures to prevent future events, etc. If the event is severe or life-threatening, then the DSMB may consider halting future injections until a best course of action is devised. If the event is an SAE that is considered severe or life-threatening, then no future patients may be injected until approved by the DSMB. In addition to the above, the DSMB will

be charged with reviewing the safety data from the first two patients injected and providing consultation on enrollment of subsequent patients.

The DSMB will be expected to advise RegenMed (Cayman) Ltd. regarding the study design and study conduct, and may recommend early study termination for safety reasons. The DSMB will be expected to request additional information and analyses as they require. The DSMB's recommendations will be communicated to the study centers, and where required to the IRBs/ECs and the Competent Authorities. If the DSMB recommends stopping the study, the Competent Authorities and the IRBs/ECs will be notified.

The surgical procedures used in this study, renal biopsy, percutaneous needle insertion in the kidney, and laparoscopic or retroperitoneoscopic surgery, are established procedures with known adverse event profiles. However, if unexpected procedure-related events occur, the DSMB will review the events on a case-by-case basis.

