13.6 Stopping Criteria

Approximately two to three weeks following each of the first two injections, the PI, Medical Monitor, DSMB and RegenMed (Cayman) Ltd. staff will review the case to assess both positive and negative results of the injection. If no clinically significant unexpected events are identified, the next patient may be injected such that the timing between the first 3 injections will be staggered by 3 weeks. If any of the following events occur, no additional patients can be injected until review by the DSMB is completed:

- 1. An SAE that is rated as severe or life-threatening and considered related to NKA or study procedures by the PI
- 2. Death of an enrolled patient
- 3. Similar SAE's in more than one patient that are considered related to NKA by the investigator
- 4. Inability to deliver a minimum of 50% of the dose of NKA in more than one patientdue to surgical or other issues
- 5. DSMB recommendation to temporarily stop enrollment to allow for more precise review of case(s)

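### After the early-case reviews, an SAE blamed on the procedure alone, of a listed kind and below severe, has no stated route to the DSMB and cannot count toward the repeat-SAE rule

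*Combined protocol and SAP*

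**What the plan says.** Section 13.5 defines what the board sees: "The specific mandate of the DSMB will be to review any AE's/SAE's assessed by the PI as related to the investigational product, NKA". The site or CRO forwards events on that basis. The section describes the surgical procedures as established, with known adverse event profiles, and adds one clause for them: "if unexpected procedure-related events occur, the DSMB will review the events on a case-by-case basis". It also gives the board a general power: "The DSMB will be expected to request additional information and analyses as they require".

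Section 13.6 lists five triggers after which "no additional patients can be injected until review by the DSMB is completed". Two of them differ in scope:

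- Item 1: "An SAE that is rated as severe or life-threatening and considered related to NKA or study procedures by the PI".
- Item 3: "Similar SAE's in more than one patient that are considered related to NKA by the investigator".

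Item 2 is the death of an enrolled patient. Item 4 is "Inability to deliver a minimum of 50% of the dose of NKA in more than one" patient. Item 5 is the board's own recommendation to stop enrollment temporarily.

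Section 13.3.4 sends every SAE up to the 18-month visit to the sponsor or its designee within 24 hours. It names no onward step to the DSMB.

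**The concern.** Item 1 covers NKA and study procedures; item 3 covers NKA only. Section 13.5 makes the same split, so that even a mild, non-serious event is forwarded if the PI calls it NKA-related, while a moderate SAE attributed to the procedure is not. Similar moderate procedural SAEs could therefore recur, perhaps with one injection approach, and no rule would require the independent board to look.

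Three features of the trial make this matter:

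- Procedure-related AEs are part of the primary safety outcome (14.3), and the synopsis names bleeding after injection as the main known risk.
- Section 6.6.2 introduces percutaneous injection in this protocol version; NKA had previously been given laparoscopically. The experience behind the known profiles comes from biopsy, ablation of renal masses and nephrectomy-type surgery, not from percutaneous delivery of NKA.
- Up to 10 centers take part, and each team selects its own method (6.5.2). A pattern may be visible only when cases are put together across sites.

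**Working it through.** The plan states no figure on this point, so the main check follows one class of event through every provision. The class is an SAE attributed to the procedure alone, of a kind listed in 13.4.1, graded below severe, after the early-case reviews.

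| Provision | Condition | Responds? |
|---|---|---|
| 13.5 mandate and forwarding | PI rates the event NKA-related | No |
| 13.5 procedure clause | Event is unexpected | No, if listed kinds are read as expected |
| 13.6 item 1 | Severe or life-threatening | No |
| 13.6 item 2 | Death | No |
| 13.6 item 3 | NKA-related | No, at any number of events |
| 13.6 item 4 | Under half the dose delivered in more than one patient | Only if that also happens |
| 13.6 item 5; 13.5 power to request data | Board's discretion | Only if the board already knows or asks |
| 13.3.4 | Any SAE | Reaches the sponsor's designee; no onward step |

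**Reading of unexpected.** Sections 13.4 and 13.5 do not define the word. Section 13.4 describes its listed events as ones already seen after these procedures, so they are read here as expected.

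**Can the class occur?** Yes, under the protocol's own rules. The planned stay after percutaneous injection is 0 to 1 night (section 9). A procedure-related AE keeps the patient in hospital until it resolves, stabilizes or returns to baseline (11.3). A complication that prolongs the stay is serious (13.1.2), while severity is graded separately (13.2.2).

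**Reach of the early-case reviews.** The board reviews the first 2 patients injected (13.5, 13.6) and the first 3 second injections (synopsis).

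- No overlap: 2 + 3 = 5 injections. If the first two patients are returning Phase 1 patients, their injections are themselves second injections, and the total is 3.
- Maximum injections: 30 × 2 = 60. If 30 patients are treated, all 7 Phase 1 patients return for one dose each, and every planned dose is given: 7 × 1 + 23 × 2 = 53.
- Even on the lower total and the wider review, 53 − 5 = 48 injections rely on the routing rules alone.

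**How often the proposed extra review would be prompted.** This sizes the cost of the fix, not harm from the gap. With p an assumed chance that a patient has a procedure-related SAE and n = 30 independent patients, P(X ≥ 2) = 1 − (1 − p)^30 − 30p(1 − p)^29.

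| Assumed rate | Rate is per patient | Rate is per procedure, three procedures each |
|---|---|---|
| 1% | 3.6% | 22.4% |
| 3% | 22.7% | 75.0% |
| 5% | 44.6% | 94.1% |

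The last column replaces p by 1 − (1 − p)^3, for a biopsy and two injections: 0.0297, 0.0873 and 0.1426. Requiring the SAEs to be similar lowers every entry. The 3% matches the figure in 13.4.1 for macroscopic hematuria and painful hematomas after biopsy, which is not an SAE rate.

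**The case against.** The strongest reply is that this is a deliberate choice with a stated reason. Severe or life-threatening procedural SAEs and deaths already halt injections, and 12.5.2 stops an injection on evidence of active bleeding. What remains is moderate, recognized complications. That narrows the class, but the stated reason does not extend to percutaneous delivery of NKA.

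A second reply turns that point round: if the approach has no established profile, its SAEs can be called unexpected and reviewed. The undefined word allows this reading but does not require it, so a site could properly withhold the event.

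Third, the relatedness scale in 13.2.1 is framed around NKA injection, and the lowest related category applies when a link seems unlikely but cannot be excluded. Section 6.2.2 reports two renal-hemorrhage deaths in a rat study of NKA or control injection. A bleed after injection could therefore be rated possibly related, which would forward it and count it under item 3. That is correct. It means routing turns on one PI label, while 13.4.2 tells investigators that no product-related events are expected.

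Fourth, the board has general oversight and may request data, and its detailed duties are left to a charter. A routine SAE listing may be there. This is the main reservation.

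Fifth, whether a bleed that prolongs the stay can grade below severe depends on CTCAE v4.03, which the documents do not reproduce. That limits what can be said about frequency, not about the routing.

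Finally, the NKA-only scope of item 3 is defensible for an automatic pause, because some procedural SAEs may be background. The remedy respects this.

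**Conclusion.** The concern holds. Read as written, sections 13.5 and 13.6 give this class no stated route to the DSMB after 3 to 5 reviewed injections, and item 3 cannot respond to it at any event rate. The class is narrow, and the documents give no rate from which to size the harm. The conclusion assumes that the kinds listed in 13.4.1 count as expected, that the PI attributes the event to the procedure alone, and that the charter adds no route. Confidence is medium for those reasons. It is worth fixing because it concerns the main known risk, and the remedy uses reports that already exist.

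**What to change.** 1. In 13.5, after the sentence on forwarding NKA-related events, add: *All SAEs assessed as related to NKA or to study procedures (biopsy or injection) will be forwarded to the DSMB as reported, whatever their expectedness or severity, with the injection approach shown.* Keep the forwarding of NKA-related AEs.
2. Leave item 3 of 13.6 as the automatic-pause rule for NKA-related SAEs. Outside the list of pause triggers, add: *Similar procedure-related SAEs in more than one patient prompt an ad hoc DSMB review; the DSMB may pause injections under item 5.*

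Mirror both sentences in the DSMB charter. If the charter already provides this, restating it in the protocol costs almost nothing. Otherwise the cost is more reading for the board and an occasional extra meeting, with the frequency depending on the assumed rates above. Because those reviews could reflect background complications, the second sentence asks for a review and not a halt.

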13.6 Stopping Criteria

Approximately two to three weeks following each of the first two injections, the PI, Medical Monitor, DSMB and RegenMed (Cayman) Ltd. staff will review the case to assess both positive and negative results of the injection. If no clinically significant unexpected events are identified, the next patient may be injected such that the timing between the first 3 injections will be staggered by 3 weeks. If any of the following events occur, no additional patients can be injected until review by the DSMB is completed:

- 1. An SAE that is rated as severe or life-threatening and considered related to NKA or study procedures by the PI
- 2. Death of an enrolled patient
- 3. Similar SAE's in more than one patient that are considered related to NKA by the investigator
- 4. Inability to deliver a minimum of 50% of the dose of NKA in more than one patientdue to surgical or other issues
- 5. DSMB recommendation to temporarily stop enrollment to allow for more precise review of case(s)

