- 22. Patients with bleeding disorders that would, in the opinion of the Investigator, interfere with the performance of study procedures; patients taking coumarins (e.g. Warfarin) or other anticoagulants (e.g. enoxaparin or direct thrombin inhibitors).
- 23. Any circumstance in which the investigator deems participation in the study is not in the subject's best interest.
- 24. Use of any investigational product within 3 months of the injection without receiving prior written consent of the Medical Monitor.

Number of Sites: Up to 10 clinical centers will be included in the study.

Study Duration: 18 months NKA injections follow up followed by 24 month long term follow up for a total study duration of 42 months.

Study Enrollment: Up to 30 subjects undergoing NKA injection will be enrolled into the study. Patients who have received a single injection of NKA under previous research protocols may enroll in this clinical trial to receive a single additional injection. Patients who have never received an NKA injection may enroll in this clinical trial for up to a total of two (2) NKA injections, temporally spaced at least 6 months apart. All biopsies are to be taken from a single kidney, and all NKA injections are to be given into the kidney that was biopsied. Patients who complete screening procedures satisfying all I/E criteria will be enrolled into the study immediately prior to the injection. Patients who do not meet all criteria before injection will be considered screen failures. Once a patient has been injected, the patient will have completed treatment and every effort should be made to ensure the patient completes all follow-up visits. Injection dates for the first 3 patients receiving their second NKA injection will be staggered by a minimum of 3 week intervals to allow for assessment of acute adverse events and other safety parameters by the DSMB. Subsequent second injections will continue to be staggered so as to occur no less than 3 weeks apart, but individual DMSB review will not be required. At the completion of the follow-up visits, patients will continue in a long-term follow-up study. Patients will be followed for a total of 36 months following the last NKA injection under this protocol, whether the first or second injection.

Investigational Plan:

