It is anticipated that all patients will be planned to receive 2 injections under this protocol, in order to allow dose-finding and to understand the duration of effect. Under certain circumstances a patient or investigator may decide to postpone or withhold the second dose. In general, if there appears to be any untoward safety risk, in situations including rapid deterioration of renal function, the development of uncontrolled diabetes, or the development of uncontrolled hypertension, or if there is the intercurrent development of a malignancy, the patient should not receive the second dose.

Second injections under this protocol will be staggered so that single injections in different patients occur no less than 3 weeks apart. The DSMB will review the clinical data regarding each of the first 3 second injections under this protocol, and will consult with the Sponsor before the 2nd, 3rd, and 4th second injections are made. Subsequent second injections will continue to be staggered so as to occur no less than 3 weeks apart, but individual DMSB review will not be required.

No staggering will be required for first NKA injections under this protocol.

Post-Injection Follow-up: Subjects will return to the clinic for follow-up safety assessments on Days 7, 14, and 28 post-injection and at 2, 3, and 6 months post-injection. At 6 months post-injection, post-treatment MRI and renal scintigraphy studies will be conducted. After patients complete the 6 month efficacy visit, they will be considered for a second NKA injection. Patients receiving a second dose will follow the same follow up visits that occurred after first injection. Patients 6 month post first injection visit will serve as the patients 14 to 10 day pre- second injection visit. Patients will return for their second injection and at 2, 3, and 6 months post-injection Patients will be followed up to 18 months in the post follow up phase with 6 months after first NKA injection and 12 months after second NKA injection. Refer to the time and events schedule on page 14 for additional post follow up time points.

Long Term Follow-up: Patients will be followed for safety and efficacy for 24 months after the 18 month initial follow up period. Telephone contact will be made 24 and 36 months after the last NKA injection, and visits will be made at 30 and 42 months after the last NKA injection.

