6 INTRODUCTION AND BACKGROUND

RegenMed (Cayman) Ltd. is a regenerative medicine company whose principals have experience in developing regenerative medicine products (Atala et al., 2006; Basu et al., 2011; Basu and Ludlow, 2012; Genheimer et al., 2012; Jayo et al., 2008a; Jayo et al., 2008b; Jayo et al., 2008c; Kelley et al., 2012; Kelley et al., 2010). RegenMed (Cayman) Ltd. is currently developing a regenerative cell-based product, Neo-Kidney Augment (NKA), designed to augment renal function in patients with chronic kidney disease (CKD). Therapeutic intervention with NKA is intended to delay the need for renal replacement therapy (dialysis or transplant) which at this time, is inevitable in patients with CKD. Therapeutic intervention with NKA entered clinical investigations with two similar Phase 1 studies, one at the Karolinska University Hospital Huddinge in Stockholm, Sweden (6 patients) and one at the University of North Carolina, Chapel Hill, NC (1 patient). To date, 7 patients have been biopsied and injected safely with NKA. This second study is designed to continue those clinical trials and assess the effect of a first and second injection of NKA in type 2 diabetic patients with CKD.

6.1Chronic Kidney Disease

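### The synopsis exempts first NKA injections from staggering, while section 13.6 staggers the first three injections of any kind

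*Combined protocol and SAP*

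**What the plan says.** **Synopsis, Study Enrollment.** The spacing is tied to the second dose: "Injection dates for the first 3 patients receiving their second NKA injection will be staggered by a minimum of 3 week intervals", so that the DSMB can assess acute safety.

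**Synopsis, Investigational Plan (Injection).** The same rule is widened to all second doses: "Second injections under this protocol will be staggered so that single injections in different patients occur no less than 3 weeks apart". The DSMB reviews each of the first three of these; later ones keep the spacing but need no individual review. First doses are then exempted: "No staggering will be required for first NKA injections under this protocol".

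**Section 13.6, Stopping Criteria.** A case review takes place "Approximately two to three weeks following each of the first two injections". If it finds no clinically significant unexpected event, the next patient may be treated, such that "the timing between the first 3 injections will be staggered by 3 weeks". A list of halting events follows, introduced by "If any of the following events occur, no additional patients can be injected until review by the DSMB is completed".

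**Section 13.5, Data Safety Monitoring Board.** The DSMB is charged with "reviewing the safety data from the first two patients injected and providing consultation on enrollment of subsequent patients".

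Sections 13.5 and 13.6 do not separate first from second injections in these sentences. Sections 9 and 11.3, which describe the design and the injection visit, do not mention staggering.

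**The concern.** Both texts are current and operative, and they differ on whether a new patient's first injection must wait for an earlier patient's result. Up to 10 centers may take part. Two sites following the synopsis could give first injections with no interval between them and so breach section 13.6.

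What would be lost is a go/no-go step. Section 13.6 lets the next patient proceed only if no clinically significant unexpected event has been found. That threshold is lower than the listed halts: a severe or life-threatening related SAE, a death, similar related SAEs in more than one patient, under-delivery in more than one patient, or a DSMB recommendation. A single moderate unexpected event could hold the next injection at the review and yet meet none of the first four halts.

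The product is not first-in-human: "To date, 7 patients have been biopsied and injected safely with NKA" (section 6). But section 6.6.2 says that this protocol version introduces the percutaneous route, whereas earlier injections were laparoscopic, and the synopsis names hemorrhage after injection as the greatest recognized risk.

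**Working it through.** The plan gives no figure to reproduce. The check sets the rules side by side and works out the minimum time each imposes.

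**1. Scope of each rule**

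| | Synopsis | Sections 13.5 and 13.6 |
|---|---|---|
| Interval | 3 weeks | 3 weeks |
| Injections covered | second injections only; first injections exempt | first three injections, type not stated |
| Scheduled review | first three second injections | first two injections (13.6); first two patients injected (13.5) |

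The interval agrees. The set of injections it covers does not.

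**2. Minimum time from first to third injection**

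Let *r* be the number of returning Phase 1 patients, receiving their second dose, among the first three people injected.

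- Section 13.6: 2 intervals × 3 weeks = 6 weeks for every *r*.
- Synopsis: only second injections are spaced, so the minimum is 3 × (*r* − 1) weeks for *r* ≥ 1, and 0 for *r* = 0.

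| *r* | Section 13.6 (weeks) | Synopsis (weeks) | Gap (weeks) |
|---|---|---|---|
| 0 | 6 | 0 | 6 |
| 1 | 6 | 0 | 6 |
| 2 | 6 | 3 | 3 |
| 3 | 6 | 6 | 0 |

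**3. Which *r* is plausible**

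- Possible returners: 6 in Sweden + 1 in the US = 7 (section 6).
- *r* = 3 is possible. Returning patients may skip the biopsy (section 4, laboratory schedule, footnote 2), while new patients wait at least 4 weeks after theirs (section 11.2). No section requires returners to go first.
- Six of the 7 depend on regulatory and ethics approval and on re-consent (section 6.3.4). As a scenario, since the order of sites is not stated: if only the US patient can return before the third injection, *r* is at most 1 and the gap is 6 weeks.
- If all 30 places are filled (section 10.1), at least 30 − 7 = 23 patients are new. This describes the trial as a whole; the conflict itself concerns only the first three injections.

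**4. Scheduled reviews if both duties are kept**

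2 (first two injections) + 3 (first three second injections) − overlap. The overlap is the number of second injections among the first two given: 0, 1 or 2. The total is 5, 4 or 3 reviews, against 3 in the synopsis alone. The review duties differ but can both be met, so they need alignment and are not a contradiction.

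**The case against.** The synopsis sentence is permissive. It says that staggering of first injections is not required; it does not forbid it. A trial run to section 13.6 would therefore breach neither text. That is correct, and it is a reason to prefer the stricter rule as the fix. It does not remove the problem, because a site told that no stagger is needed has no instruction to apply one.

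The sponsor also controls timing. Product is made only after the site confirms eligibility at the visit 10 to 14 days before injection (sections 8.2.2, 9 and 11.3), and sponsor staff take part in the section 13.6 reviews. This makes an unnoticed breach less likely, but the sponsor still has to know which rule governs.

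The table counts a returning patient's injection as a second injection. Read literally, the synopsis phrase about second injections under this protocol could exclude it, since it is that patient's first injection in this trial. The synopsis minimum would then be 0 weeks for every *r*, and the gap always 6. The Study Enrollment and Biopsy paragraphs of the synopsis and sections 8.2.1 and 9 treat a returner's injection as the second, so the table follows the better-supported reading.

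Section 13.6 may have been meant for second injections only. Its text does not say so, and even then it would review two cases against three in the synopsis. The section 13.6 stagger is also not specific to route, so all three spaced cases could be laparoscopic; the new percutaneous route adds only modest weight.

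**Conclusion.** The inconsistency is real: the synopsis and section 13.6 set different requirements for first injections among the first three given, and no section reconciles them. The difference in minimum time from first to third injection is 6, 6, 3 or 0 weeks for 0, 1, 2 or 3 returning patients. This assumes that a returner's injection counts as a second injection; on the literal alternative it is 6 weeks throughout. There is no practical effect if the first three people injected are all returners, on the reading used here.

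The consequence is confined to early safety conduct. The event-triggered halts in sections 13.5 and 13.6 apply under either rule, and no endpoint, analysis set, sample size or error rate changes. The DSMB charter was not available; it may clarify intent, but it would not remove conflicting instructions from the protocol. The point should be fixed.

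**What to change.** **Preferred: keep the stricter rule, which satisfies both texts.**

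- Narrow the synopsis exemption, for example: *First injections need not be staggered once the third injection of the study has been given.*
- State in section 13.6 that the 3-week stagger covers the first three injections, whether first or second doses, with DSMB review after each of the first two.
- Leave the synopsis rule for second injections as it stands.
- Repeat the same rule, with the number of cases reviewed, in section 13.5 and the DSMB charter.

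**Alternative: if the sponsor intends the synopsis rule alone,** amend sections 13.5 and 13.6 to refer to second injections and to three reviewed cases. New patients' first injections would then have no planned pause.

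**Cost of the preferred option.** Wording in the synopsis, sections 13.5 and 13.6, and the charter. The first three injections take at least 6 weeks, which is 0 to 6 weeks more than the synopsis rule. Scheduled reviews total 3 to 5, which is 0 to 2 more than the synopsis; sections 13.5 and 13.6 already ask for the two early ones. No extra patients, visits or procedures.
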